## Abstract

Certain mood stabilizer/anticonvulsant medications may be better suited for epilepsy with comorbid psychiatric illness. Many anticonvulsants are broad-spectrum and are well established as improving outcome for epilepsy as well as for behavioral disorders. The intuitive choice for treatment in patients with such comorbidity would be medications with an established track record in successfully treating both conditions independently. Benzodiazepines are a mainstay of anxiety treatment as well as for epilepsy treatment.

Given its unique molecular structure, clobazam (Onfi®) is an example of a medication that theoretically could serve a “dual role” in terms of treating epilepsy as well as anxiety disorder. Anxiety is prominent in children and adolescents with epilepsy although the evidence base is underdeveloped.

This study would assess the utility of clobazam, which may represent a more effective and better tolerated treatment option for the numerous patients with seizure disorders who also have anxiety. This study is an investigator initiated proposal submitted by the PI and is a prospective open-label clinical trial of 20 children and adolescents with epilepsy. The assessments include standardized questionnaires widely used in clinical practice as well as structured psychiatric diagnostic tools. Overall, this study will contribute valuably to an understudied patient population and add key information to the evidence base that potentially will make an immediate clinical impact.

## Overview of Study Design

This study is an open label, adjunctive, proof of concept, pilot clinical trial. Prospective participants will be identified from chronic epilepsy clinical populations of Johns Hopkins Hospital and Kennedy Krieger Institute. Pediatric participants will be considered for the study if neurologic status suggests the need for additional treatment, and behavioral characteristics are clinically significant. All participants will receive active treatment, involving flexible dose titration of clobazam and will be monitored for a period of four months. The study will be monitored and overseen by the Johns Hopkins Hospital Institutional Review Board.

## Study Population

Prospective research participants will be identified from the chronic epilepsy clinic population of the Neurology Departments of Johns Hopkins Hospital and Kennedy Krieger Institute in addition to clinic populations recruited in the region. Pediatric participants will be recruited between the ages of 6 and 17 years, inclusive, in order to allow valid completion of behavioral measures. No exclusion will be made on the basis of gender or minority status.

Participants will be considered for the study if anxiety disorder symptoms appear to be prominent in children and adolescents with existing epilepsy. Subjects will be included in the study if they fulfill diagnostic criteria for an anxiety disorder with functional impairment.

## **Study Visits**

After initial telephone contact and pre-screening is completed, the screening study visit will be scheduled. At that visit, study details will be reviewed and informed consent will be obtained by the PI. The screening study visit will include detailed medical and psychiatric history review, pertinent, physical examination (vital signs, neurologic exam), and assessment including semi-structured diagnostic interviews and rating scales.

Following the screening visit, participants who qualify and continue consent will enter into the active treatment phase of the study. The initial treatment phase will begin with a dispensing visit. It is expected that the dispensing visit may occur on the same day as the screening visit. However, if it does not occur on the day of the screening visit, it may occur within two weeks of the screening visit.

Continued contact with research participants will be done at regular intervals over a period of approximately 4 ½ months. In-person visits will occur biweekly for the first six weeks. In-person visits will occur monthly for the next two months. A total of seven in-person visits will occur including the baseline or screening visit. Participants who will continue on the drug, managed by their primary clinician, may have their care transitioned to their primary clinician before the time frame of the seventh in-person study visit.

At each contact, inquiry regarding adverse events, physical and mental health status, and compliance with treatment will take place. Safety assessment including mental health status and seizure diary review will take place at each subject contact. Safety assessment will include assessment of suicidal thoughts or actions. The PI will be involved with safety assessment at all study visits for each participant.

Telephone contacts will also be arranged at weeks 8, 12 and 16 to assess safety, adverse events and tolerability. Subject contact will occur every two weeks for the duration of the study.

All participants will receive adjunctive clobazam as active treatment. Initial titration will occur at standard dosage schedules, expected to be 5-10mg daily with 5-20mg biweekly increases. Increases may progress to a total of 40 mg daily, either in single dosages or divided dosages. Mimicking clinical practice, a flexible dose paradigm will be utilized to allow titration to effect and mitigation of

potential adverse events. Flexibility with minimum or maximum dosages will be employed in order to meet clinical needs.

Participants will be considered to have completed the study if they have successfully completed in-person visits. Participants will be free to withdraw from the study at any time by their choice, or if adverse events are intolerable or other risks outweigh potential benefits then participants will be terminated from the study. Participants who withdraw early for any reason will be assessed for safety, discharged from the study and returned to the care of their primary neurologist.

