#### **Statistical Analysis Plan**

Change from baseline will be analyzed statistically to test the main study hypotheses--that Onfi® has a dual role of improving both behavioral/psychiatric status, namely anxiety symptoms, as well as seizure control, in patients with epilepsy.

Outcome measures will encompass behavioral and neurologic status. The primary outcome variable will be Clinical Global Assessment of Functioning Improvement from baseline. CGI ratings will be attributed both to neurological status including seizure control, as well as behavioral status. CGI-Improvement ratings of a 1 or 2 (on a 7 point scale) will be considered positive responses. Paired student's t-tests will be used to compare baseline and study endpoint ratings for response versus non-response.

Secondary outcome measures will include changes from baseline in overall and subscale ratings of the Pediatric Anxiety Rating Scale (PARS), Multidimensional Anxiety Scale (MASC), and the Quality of Life in Epilepsy Scale. Positive outcomes will be defined as 10% score reduction or scores that drop below threshold of clinical significance. Paired student's t-tests will be used to compare baseline and study end outcomes for each measure.

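### Early withdrawals get only a safety assessment, and the paired analyses have no analysis set or rule for unrated participants, so withdrawals can drop out of the efficacy results

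*Combined protocol and SAP*

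**What the plan says.** The Statistical Analysis Plan is one short section. For the primary outcome, with a CGI-Improvement rating of 1 or 2 counted as response, it states: "Paired student's t-tests will be used to compare baseline and study endpoint ratings for response versus non-response". For PARS, MASC and quality of life it states: "Paired student's t-tests will be used to compare baseline and study end outcomes for each measure". It adds a responder-type definition for those scales, "Positive outcomes will be defined as 10% score reduction or scores that drop below threshold of clinical significance", without a denominator. It ties neither the endpoint nor the study end to a visit, defines no analysis set, and does not say how a missing end rating is handled.

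Study Visits lets participants leave by choice and has them terminated for intolerable adverse events or an unfavourable balance of risk and benefit. On what happens at that point it says: "Participants who withdraw early for any reason will be assessed for safety, discharged from the study". They then return to their neurologist.

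The same section mentions rating scales only for the screening visit: "assessment including semi-structured diagnostic interviews and rating scales". For later contacts it says: "At each contact, inquiry regarding adverse events, physical and mental health status, and compliance with treatment will take place", and "Safety assessment including mental health status and seizure diary review will take place at each subject contact". None of the four efficacy instruments is named there.

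**The concern.** A paired test uses only people with both values. If no efficacy rating is required at exit and no rule covers its absence, the default is an analysis of those who stayed. Poor tolerability is a stated ground for leaving, and lack of benefit is a plausible one, so those who stay are likely to be a favourable selection. In a single-arm study there is no control group against which such selection might show.

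Two features make this more than a gap in drafting. A rating not taken when the participant leaves cannot be recreated at analysis. And the study is open label, so with no rule fixed in advance, who is counted could be settled after results are known.

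**Working it through.** **No plan figure to reproduce.** The documents give a sample size but no power, response rate or dropout rate.

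**Inputs.** N = 20 (Abstract). Response is CGI-Improvement of 1 or 2 (Statistical Analysis Plan). The number unrated, m, and the number of rated responders, r, are assumptions.

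**Response rate: formulas.**
- Rated only: r/(N − m).
- All treated, worst case (all unrated are non-responders): r/N.
- All treated, best case (all unrated are responders): (r + m)/N.
- Width of the bounds: m/N, or 1/20 = 5 percentage points per unrated person.
- If all unrated are non-responders, rated-only rate ÷ all-treated rate = N/(N − m), whatever r is.

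| m | Width of bounds | N/(N − m) |
|---|---|---|
| 1 | 5 points | 20/19 = 1.05 |
| 2 | 10 points | 20/18 = 1.11 |
| 4 | 20 points | 20/16 = 1.25 |

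**Example with r = 8, m = 4** (exact 95% intervals):
- Rated only: 8/16 = 50.0% (24.7% to 75.3%).
- Worst case: 8/20 = 40.0% (19.1% to 63.9%).
- Best case: 12/20 = 60.0% (36.1% to 80.9%).

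**Mean change on the secondary scales.** If the unrated would have had on average a fraction f of the rated mean change, the rated mean is 20/(20 − m + m·f) times the all-treated mean. For m = 4:
- f = 0: 20/16 = 1.25
- f = 0.5: 20/18 = 1.11
- f = 1: 20/20 = 1.00
- f = 1.5: 20/22 = 0.91

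The rated mean is too favourable only if those who leave do worse.

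**Can the endpoint be read off the visit schedule?** Study Visits states seven in-person visits including screening. Screening, two-weekly visits for six weeks and monthly visits for two more months give weeks 0, 2, 4, 6, 10 and 14, which is six. Two readings reach seven:
- A separate dispensing visit is the seventh, and the last visit is at about week 14.
- A further visit falls at about week 18. This fits the calls at weeks 8, 12 and 16, the two-weekly contact, and a duration of about 4½ months (4.5 × 52/12 = 19.5 weeks), but not two months of monthly visits.

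The text does not settle which is meant.

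**The case against.** **Exit ratings are possible under the plan.** Nothing forbids them, and mental health status and the seizure diary are reviewed at every contact, which could inform a global rating. The protocol also schedules no post-baseline efficacy rating for completers, although the analysis plainly needs one, so silence at withdrawal is partly a general lack of an assessment schedule. This stands, and it limits the claim to what can happen. It does not remove the gap: for withdrawals the protocol does say what is done, and no efficacy rating is part of it.

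**The size is assumed, and sampling error is larger.** In the example, the 40% to 60% bounds lie inside the 24.7% to 75.3% interval for 8/16. True; but the interval shows sampling error, whereas loss of withdrawals from the denominator shifts the estimate without showing in it.

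**The illustration is not the written analysis.** The plan specifies a paired t-test, not a proportion with an exact interval. Also true, and the reason that the fix names the summary to be used.

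**It is only a pilot.** Fair as to the amount of machinery wanted. But the plan says that it will test its main hypotheses statistically, and in 20 people each missing rating counts for more.

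A reader might go further and infer that participants who continue the drug under their own clinician go unrated, which would bias results downward. The text says only that they "may have their care transitioned to their primary clinician before the time frame of the seventh in-person study visit". That describes a transfer of care and does not say that the visit is skipped, so no direction of bias can be drawn from it.

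**Conclusion.** The point holds and should be fixed. The plan requires no efficacy rating at early withdrawal, defines no analysis set and gives no rule for unrated participants, so following it literally can produce a completers-only result that cannot be repaired later. Confidence in the omission is high.

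The consequence is conditional. A favourable bias rests on the assumption, plausible from the stated grounds for termination but not quantified anywhere, that those who leave do worse. The figures (5 points per unrated person; a ratio of 1.25 if 4 of 20 are unrated non-responders) show sensitivity and are not predictions.

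The documents do not support the stronger readings that withdrawals will be excluded, that exit ratings are ruled out, or that the results are biased by a known amount. Nor is the visit count an outright error: it is an ambiguity that leaves the last visit unidentified.

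**What to change.** 1. **Study Visits:** add CGI-Improvement, PARS, MASC and quality-of-life ratings at the last contact for anyone who leaves before the final in-person visit.
2. **Statistical Analysis Plan, primary:** report the proportion of all participants who took at least one dose with CGI-Improvement of 1 or 2, with an exact 95% confidence interval. Use the endpoint rating, otherwise the exit rating, and count anyone with no post-baseline rating as a non-responder.
3. **Statistical Analysis Plan, reporting:** give the number unrated and the worst/best-case bounds on response. For the secondary scales, report mean change in participants with an endpoint or exit rating. Do not assign zero change to the unrated, because imputing a constant can understate the variance that the paired test uses.
4. **Endpoint:** tie the study endpoint to the final in-person visit, and reconcile the visit descriptions so that its week is clear.

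The cost is some wording and one set of existing instruments at exit. Exit ratings will fall at differing times, some during titration, so they behave like last-observation values. Some may need separate arrangement, because the protocol does not say that the exit assessment is in person. Counting the unrated as non-responders is conservative, and the headline response rate may be lower.

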**Inclusion criteria:**

- Established diagnosis of epilepsy, characterized by focal seizures with suspected or documented localization in the temporal lobe. All participants will have active epilepsy that requires treatment with anticonvulsant medication.
  - Although it is not necessary to be seizure free, a seizure baseline period will be established in the 60 days prior to enrollment into the study.
  - Current regimen of anticonvulsant drugs must have been stable for 30 days prior to entry into the study.
- No episodes of seizure clusters of status epilepticus within 30 days prior to entry into the study.
- Established symptoms of anxiety with functional impairment.
- Baseline behavioral criteria for inclusion will include subscale scores above the norm for age and gender on one of the following:
  - Pediatric Anxiety Rating Scale (PARS).
  - Multidimensional Anxiety Scale (MASC)
- Male or female participants equal to or above age 6 and below age 18 at the start of the study. No exclusion will be made on the basis of gender or minority status.
- Good general health as determined by medical history and physical examination.
- Ability to swallow pills (participant will receive pill swallowing instruction if necessary). The medicine may be cut into pieces and/or mixed with applesauce.
- If female of childbearing age, a negative urine or serum pregnancy test must be established or assured at baseline. Additionally, the participant must agree to use abstinence or appropriate contraception methods or be otherwise incapable of pregnancy for the duration of the study. Pregnancy test results will be shared with parent or guardian. Pregnancy status (or prevention) and abstinence or contraception methods will be addressed

throughout the study for females of childbearing age as well as for post-pubertal males.

- Previous subjects who failed at any point to meet continuation criteria and withdrew early may be considered for re-enrollment by the PI on a case-by-case basis.
- Participant or legal caregiver capable of providing informed consent and fully capable of monitoring the subject's disease process and compliance with treatment.

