## Risks

The clearest risk is of potential side effects or other adverse effects of clobazam (Onfi®) drug treatment. Clobazam is a widely available anticonvulsant medicine with FDA indication for seizures associated with Lennox Gastaut Syndrome in pediatrics. All participants will have active epilepsy that requires treatment with anticonvulsant medication, so the risks incurred with drug treatment are equivalent to that experienced in typical neurologic clinical care for epilepsy. Close clinical monitoring and active side effect and adverse event monitoring at each contact will minimize risks due to drug side effect.

Specific risks notable for clobazam include rare but serious skin reactions, called Stevens-Johnson and toxic epidermal necrolysis. The skin reaction is very rare, but more likely to occur within the first 8 weeks of treatment or if clobazam is stopped and then restarted. Participants will be instructed to contact the 24 hour information line or emergency health care services for any occurrence of skin rash. In this circumstance, sudden stoppage of the medication is indicated.

Like other antiepileptic drugs, The U.S. Food and Drug Administration has reported that anticonvulsants including clobazam may increase the risk of suicidal thoughts or behaviors in a very small number of people taking the drug. Participants will be closely monitored for depression, suicidal thoughts or behavior, and unusual changes in mood or behavior. Psychiatric assessment will occur on each contact with participants to address this potential adverse reaction.

Clobazam may slow thinking and impair motor skills; so participants will be cautioned not to drive, operate heavy machinery, or engage in other dangerous activities until they know how the drug affects them. Given its structural similarity to other benzodiazepines, clobazam can also theoretically cause abuse and dependence. It has been categorized as a Schedule IV drug under the Controlled Substances Act, and thus should not be discontinued suddenly. Onfi should not be discontinued suddenly. Stopping clobazam suddenly can cause serious withdrawal problems, such as seizures that will not stop, hallucinations, shaking, nervousness, and stomach or muscle cramps.

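### A child who stops clobazam on leaving the study early has no planned study contact after discharge, so withdrawal events may go unrecorded

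*Combined protocol and SAP*

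**What the plan says.** The combined protocol and SAP deals with early exit under Study Visits. Participants may leave by choice, and "if adverse events are intolerable or other risks outweigh potential benefits then participants will be terminated from the study". Whatever the reason, early leavers "will be assessed for safety, discharged from the study and returned to the care of their primary neurologist".

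The same section sets the contact schedule. "A total of seven in-person visits will occur including the baseline or screening visit", and "Telephone contacts will also be arranged at weeks 8, 12 and 16 to assess safety, adverse events and tolerability". It adds: "Subject contact will occur every two weeks for the duration of the study".

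The Risks section says that clobazam should not be stopped abruptly and lists serious withdrawal effects, among them seizures that do not cease, hallucinations and shaking. It makes one exception. For skin rash, families are told to use a 24-hour line or emergency care, and "In this circumstance, sudden stoppage of the medication is indicated".

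The Costs section supplies study drug free only while the child is in the study. It promises efforts to continue treatment together with the child's clinical team.

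**The concern.** Every participant has active epilepsy that needs drug treatment, and the dose may reach 40 mg daily. The protocol itself identifies withdrawal as a serious hazard, and in one situation it requires the kind of stop that it warns against. A withdrawal event needs time after the last dose to appear, but the scheduled contacts belong to study participation, which ends at discharge. A withdrawal seizure in a child who has just left could therefore happen without the study learning of it. At stake are the completeness of the adverse-event record and the study's chance to help manage such an event.

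**Working it through.** No formula applies, and the plan states no figure to reproduce. The check sets the relevant provisions side by side.

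1. **Exit procedure (Study Visits).** The sequence is safety assessment, discharge, return to the neurologist. The text does not say how many assessments are made, when they fall relative to the last dose, or whether any dose reduction comes before discharge.
2. **Contact schedule (Study Visits).** Visits, the calls at weeks 8, 12 and 16, and the two-weekly contacts are all part of study participation. None is assigned to a discharged child.
3. **Other sections.** The rest of the available text contains no call or visit after discharge, no adverse-event window after the last dose, and no request that the neurologist report back. It gives no taper schedule. The 24-hour line is mentioned only for rash and depends on the family calling. Planned study contacts after early discharge: 0.
4. **Hazard (Risks).** Abrupt cessation is described as dangerous, but no period is given in which withdrawal effects would appear. That they would fall after discharge is therefore an inference.
5. **Who is affected.** Leaving the study is not the same as stopping the drug. The gap concerns children who do both.
   - *Exit for rash:* the stop is abrupt by instruction, so the inference is most direct. The plan does not say that a rash stop always ends participation. If the child stayed in the study, the two-weekly contacts would still apply.
   - *Exit for another adverse event or by choice:* the dose may be reduced first, so the inference is weaker.
   - *Exit with treatment continued by the neurologist:* no stop occurs at exit, and this point does not apply.
6. **Size.** The Abstract plans 20 children. The documents give no rate of early exit. Assuming 1 to 5 children leave early and stop: 1/20 = 5% and 5/20 = 25%. At one call each, that is 1 to 5 calls. The ceiling is 20 × 1 = 20 calls, if every child left early and stopped; the floor is 0.
7. **Effect on the analysis.** The Statistical Analysis Plan section covers global improvement, anxiety scales and quality of life. It defines no safety analysis, so no stated analysis is biased by the missing information.

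**The case against.** The strongest case on the other side is that the child is clinically protected and the affected group is small. Exit includes a safety assessment and an active hand-over to a neurologist. Routine care continues throughout, recruitment draws largely on the two study institutions' own clinics, and the only abrupt stop that the plan directs is for rash, where families already have an emergency route. In a 20-child open-label pilot of a marketed drug, some would call a further call optional. Most of this stands. It limits the point to what the study itself records and follows up, but it supplies no study contact and no reporting route back to the study.

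Three stronger readings are tempting but unsupported.

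- **That the plan allows a single assessment and then an unmanaged stop.** The text neither limits the number of assessments nor rules out a taper before discharge.
- **That the gap undermines re-enrollment.** The plan says "Previous subjects who failed at any point to meet continuation criteria and withdrew early may be considered for re-enrollment by the PI", and the Risks section calls the serious skin reaction "more likely to occur within the first 8 weeks of treatment or if clobazam is stopped and then restarted". But a returning child would appear to face the ordinary entry checks: a 60-day seizure baseline, no seizure clusters or status epilepticus in the previous 30 days, a detailed history, and exclusion for prior hypersensitivity. A rash that caused the exit would ordinarily be known at exit. The missing call adds little to that decision.
- **That completers are equally exposed.** The week-16 call or the seventh visit may already follow their last dose, so the documents do not establish a gap for them.

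**Conclusion.** The point holds as a gap in safety follow-up and adverse-event capture for children who stop clobazam at early exit, and most clearly for a child who leaves because of rash. The number of study contacts planned after discharge is 0. The number of children affected is unknown; 1 to 5 of 20 is an assumption, and the documents give neither a withdrawal rate nor a withdrawal window.

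A reader might infer that these children are left without care or that the efficacy results are distorted. Neither follows: the neurologist takes over, and no planned analysis uses the missing information. The conclusion rests on the protocol text available and on the inference that some withdrawal effects would appear after discharge. This is a modest point with an inexpensive remedy.

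**What to change.** Add to the early-withdrawal paragraph under Study Visits, in words such as these: *Any participant who withdraws or is terminated early and stops clobazam, and whose family agrees to further contact, will receive one telephone safety contact about two weeks after the last dose. Adverse events and seizure-diary entries since the last dose, the date of the last dose, and whether the stop was abrupt will be recorded and reported separately as post-discontinuation events.*

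Two weeks is the plan's own contact interval. Since the documents give no withdrawal window, the investigator may have clinical reason to choose another time.

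The cost is at most one extra call per child who stops, no more than 20 in all, by the telephone method already in use, with no new visits. A small change to protocol and consent wording would need IRB review. The tolerability record may look less favourable. The call detects withdrawal events and helps in managing them, but does not prevent them, and it does not reach a child whose neurologist stops the drug after hand-over.
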